**1.7.3 Rationale for Expansion Cohort**

Based on initial portion of the study where the first 18 evaluable patients were investigated, a striking difference between overall response rates in ER-positive and TNBC was observed (Table 1). The ORR in ER-positive was 0%, and in TNBC it was 42.9%. Furthermore, the TNBC group had 2 patients with SD (clinical benefit rate of 71.4%), and one of the patients listed as PD, in fact had pseudoprogression (after 2 months had sub-centimeter LNs enlarge to >15mm, captured as PD per RECIST, but afterwards experience stability in these lesions, and a PR in target lesions). While the numbers are small, there is a clear signal in the TNBC cohort since essentially 6 out of 7 patient experienced clinically relevant benefit. Immunotherapy is rapidly evolving in breast cancer, and these initial results show promise in this cohort of patients, and the rationale of the expansion cohort is to capitalize on this initial experience.

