### **2.2 Secondary Objectives & Endpoints**

2.2.1 To evaluate PFS and OS in patients with metastatic HER2 negative breast cancer treated with durvalumab in combination with tremelimumab.

Secondary endpoints include PFS and OS, where PFS is defined as the time from date of treatment initiation to date of documented disease progression or death (by any cause in the absence of progression), and OS is defined as the time from date of treatment initiation until death due to any cause.

2.2.2 To evaluate safety and tolerability.

The endpoints will be the number, frequency, and severity of adverse events (as defined by the NCI Common Terminology Criteria for Adverse Events or CTCAE version 4.03) will be recorded.

2.2.3 To evaluate clinical benefit rate in this population.

Clinical benefit rate is defined as stable disease (SD) for  $\geq$  12 weeks + PR + CR.

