 The same modality used at baseline should be used throughout. CT must have contrast, MRI with contrast is acceptable alternative if the patient is allergic to CT contrast. Scans are required to be completed every 8 weeks, regardless of drug holds or treatment delays.

(Note: Bone scans will be done only if the patient has bone disease. PET-CT is acceptable in place of bone scan, if a bone scan is contra-indicated for a patient's disease. The same modality used at baseline should be used throughout.) For patients with skin lesions, photographs may be taken on study-provided camera by study staff on a white background (wall of patient room) using a ruler measurement on a study supplied digital camera. Photographs should not include any identifying characteristics. (Please refer to section 6.1.1 for details)

 Urinalysis will include color, appearance, specific gravity, pH, protein, glucose, ketones, blood, bilirubin, and microscopy including WBC/high power field (HPF), RBC/HPF.

 Serum beta-human chorionic gonadotropin (at screening only) for females of child-bearing potential (as indicated) within 7 days of registration.

 Serum Chemistry Panel will include calcium, chloride, magnesium, creatinine, sodium, potassium, blood urea nitrogen, bicarbonate, glucose, total bilirubin, aspartate aminotransferase (AST), alanine aminotransferase (ALT), alkaline phosphatase (ALP), albumin, total protein and creatinine clearance. If Total bilirubin is  $\geq 2 \times \text{ULN}$  (and no evidence of Gilbert's syndrome) then fractionate into direct and indirect bilirubin. Additional chemistry labs will include: lactate dehydrogenase (LDH), GGT, lipase, uric acid and amylase. During combination therapy, these labs should be monitored prior to each dose; during maintenance monotherapy, labs should be monitored every 8 weeks.

 Hematology will include basophils, eosinophils, lymphocytes, platelet count, monocytes, neutrophils, red blood cell count, total white cell count, hematocrit, mean corpuscular hemoglobin, mean corpuscular hemoglobin concentration, mean corpuscular volume, and hemoglobin.

 Coagulation parameters will include prothrombin time, partial thromboplastin time, and fibrinogen.

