#### 6.1.4 Immune-related RECIST

In addition to above, tumor response will be assessed by the irRECIST for investigational purposes, not assessment of primary objective (25). Tumor response by irRECIST is defined as an immune-related PR (irPR) or CR (irCR) over a period of at least 4 weeks. We will define immune-related clinical benefit rate as immune-related stable disease (irSD), irPR, or irCR.

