### 6.3 Secondary Endpoints

Secondary endpoints include PFS and OS, where PFS is defined as the time from date of treatment initiation until date of documented disease progression or death (by any cause

in the absence of progression), and OS is defined as the time from date of treatment initiation until death due to any cause.

Clinical benefit rate will be assessed and defined as SD (for  $\geq$  12 weeks) + PR + CR. Any patient who has completed two months of study therapy is evaluable for this end point

The number, frequency, and severity of adverse events (as defined by the NCI Common Terminology Criteria for Adverse Events or CTCAE version 4.03) will be recorded. Any patient treated with minimum 1 dose of either study drug will be evaluable for toxicity.

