### **10.0 STATISTICAL CONSIDERATIONS**

#### **10.1 Study Design/Study Endpoints**

This will be a single-arm, open-label, pilot phase II study to assess the efficacy and safety of durvalumab in combination with tremelimumab in patients with stage IV breast cancer which is HER2 negative. Patients who have completed the week 16 CT or nuclear bone scan will be evaluable for response endpoints. (*Note: Bone scans will be done only if the patient has bone disease. PET-CT is acceptable in place of bone scan, if a bone scan is contra-indicated for a patient's disease. The same modality used at baseline should be used throughout.*)

The **primary endpoint** is ORR, defined as number (%) of patients with at least one visit response of partial response (PR) plus complete response (CR) in patients with metastatic HER2 negative breast cancer treated with durvalumab in combination with tremelimumab using the Response Evaluation Criteria in Solid Tumors (RECIST) Version 1.1 (23). Any patient who has completed two months of study therapy is evaluable for this end point.

**Secondary endpoints** include PFS and OS, where PFS is defined as the time from date of treatment initiation until date of documented disease progression or death (by any cause in the absence of progression), and OS is defined as the time from date of treatment initiation until death due to any cause. Clinical benefit rate (SD for  $\geq$  12 weeks + PR + CR) will be assessed. Any patient who has completed two months of study therapy is evaluable for this end point.

The safety endpoints will be the number, frequency, and severity of adverse events (as defined by the NCI Common Terminology Criteria for Adverse Events or CTCAE version 4.03) will be recorded. Any patient treated with minimum 1 dose of either study drug will be evaluable for toxicity.

The expansion cohort will follow a similar design but only include patients with metastatic TNBC. Responses will be captured by RECIST v1.1.

**Exploratory endpoints** include serum and tissue-based biomarkers including: circulating tumor DNA, immunohistochemical expression of PD-L1; TILs; changes in tissue and peripheral T cell receptor sequencing, mutational and neoantigen burden, and immune-related candidate gene signatures at baseline.

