#### **10.2**

#### **Sample Size and Accrual**

A total of 35 patients (as needed) with metastatic breast cancer which is HER2 negative will be enrolled into this study and receive durvalumab in combination with tremelimumab, in order to get 28 evaluable for response. 15 patients with ER-positive disease and 15 patients with ER-negative disease will be enrolled (i.e. 2 cohorts with 14 evaluable each). Patients who have completed the week 8 CT or nuclear bone scan will be evaluable for response endpoints. Bone scans will be done only if the patient has bone disease. PET-CT is acceptable in place of bone scan, if a bone scan is contra-indicated for a patient's disease. The same modality used at baseline should be used throughout.

Using a Simon's two-stage design, we assume the undesirable overall response rate (null hypothesis) to be approximately 10%, and the alternate hypothesis to be approximately 30% based on previously published and presented data. Eleven patients will be added in the first stage. If 2 or more respond, then an additional 16 patients will be added for a total of 27. If 6 or more respond, then the hypothesis that the response rate is at least 30% is supported. This design has a Type I error rate of 4% and 80% power, and has a 70% chance of stopping early for futility after the first stage if the true response rate is 10%. The design is based on the complete sample and is not stratified by estrogen receptor status. ORR will also be calculated separately by receptor status, but the study is not powered for analyses within these subgroups.

For the expansion cohort we expect the ORR based on RECIST v1.1 to exceed 30% given our preliminary data. Using a Bayesian design assuming a prior beta distribution with parameters 0.3 and 0.7, there is a posterior probability of 0.81 that the ORR exceeds 30% if 8 or more responses out of 20 evaluable patients are observed.

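### Clinical benefit rate: the 12-week stable-disease threshold falls between scheduled scans, the denominator can drop early failures, and the interim figures use a 2-month threshold

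*Combined protocol and SAP*

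**What the plan says.** Section 2.2.3 opens with "Clinical benefit rate is defined as stable disease (SD) for" at least 12 weeks, plus PR and CR. Sections 6.3, 10.1 and 10.3 repeat the 12-week requirement.

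On timing, footnote 1 to the table in section 5.0 says "Scans are required to be completed every 8 weeks, regardless of drug holds or treatment delays". That table marks imaging at screening, week 8, week 16, week 24 and off treatment, and its notes continue scans every 8 weeks. None is scheduled at week 12.

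On who counts, the plan gives several rules:
- Sections 6.3 and 10.1, for CBR: "Any patient who has completed two months of study therapy is evaluable for this end point".
- Section 10.1, for response endpoints in general: "Patients who have completed the week 16 CT or nuclear bone scan will be evaluable for response endpoints".
- Section 10.2, for the same endpoints: "Patients who have completed the week 8 CT or nuclear bone scan will be evaluable for response endpoints".
- Section 4.9 leaves patients who miss the 2-month imaging out of ORR, PFS and OS unless the reason is clinical progression. It does not mention CBR.

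The rationale for the expansion cohort (1.7.3) cites a "clinical benefit rate of 71.4"% in TNBC. The accompanying table builds its CBR row from PR plus a row for SD of at least 2 months.

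**The concern.** Three things are unsettled for a stated secondary endpoint.

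1. **Classification.** Twelve weeks cannot be read off an 8-week scan grid without a convention. The plan does not say whether SD runs to the last scan showing SD or to the date of PD. Nor does it say how to classify SD at week 8 with no later scan.
2. **Denominator.** A rule based on completing two months of therapy excludes, on its face, treated patients who progress or die before then. These patients are failures for CBR, so removing them can only raise the rate. The week 8 and week 16 sentences add two further possible denominators.
3. **Interim figures.** The CBRs supporting the expansion cohort use a shorter SD threshold than the endpoint whose name they carry.

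If these stay open, the classification of some patients can be chosen after the data are seen. Section 10.3 also uses clinical benefit as an outcome in the biomarker analyses, so the same ambiguity carries over to them.

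**Working it through.** **Step 1. Reproduce the interim figures.** Inputs are the counts in the 1.7.3 table. Formula: CBR = (PR + SD of at least 2 months) / n.
- All: (3 + 4)/18 = 38.9%
- TNBC: (3 + 2)/7 = 71.4%
- ER+: (0 + 2)/11 = 18.2%

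All three match the table, so the threshold used is about 8 weeks, not 12. PR, SD and PD sum to n in each column (3 + 4 + 11 = 18; 3 + 2 + 2 = 7; 0 + 2 + 9 = 11), so no patient is left unclassified.

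**Step 2. Bound the defined endpoint.** Let k be the number of those SD patients who meet the 12-week requirement. CBR = (PR + k)/n, with k from 0 to the SD count. Exact binomial 95% intervals, as planned in 10.3, are in brackets.

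| Group | k = 0 | All SD kept |
|---|---|---|
| All | 3/18 = 16.7% (3.6–41.4) | 7/18 = 38.9% (17.3–64.3) |
| TNBC | 3/7 = 42.9% (9.9–81.6) | 5/7 = 71.4% (29.0–96.3) |
| ER+ | 0/11 = 0% (0–28.5) | 2/11 = 18.2% (2.3–51.8) |

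With one SD patient kept, TNBC is 4/7 = 57.1% and ER+ is 1/11 = 9.1%. The stated figures are the right-hand column, that is, the upper bounds. An SD patient falls out only by progressing before week 12, by having PD at week 16 when SD is counted to the last scan showing it, or by having no later scan and being counted as a failure.

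**Step 3. Place the threshold on the scan grid.** Twelve weeks is 12 × 7 = day 84. The scans are at 8 × 7 = day 56 and 16 × 7 = day 112, each ±3 days. The threshold is the midpoint: (56 + 112)/2 = 84.

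| Patient without CR/PR | SD timed to last SD scan | SD timed to PD date |
|---|---|---|
| SD at week 8, PD at week 16 | 8 weeks: no benefit | 16 weeks: benefit |
| SD at week 8, no later scan | 8 weeks: no benefit | unknown |
| SD at weeks 8 and 16 | at least 16 weeks: benefit | at least 16 weeks: benefit |

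**Step 4. Size the denominator effect.** Suppose m of n treated patients fail before two months and are dropped. CBR then changes from x/n to x/(n − m), a factor of n/(n − m). The documents do not give m. As an illustration only, take the plan's allowances between enrolled and evaluable patients and assume that the whole gap is early failures. With 30 enrolled for 28 evaluable (Study Summary, 3.0), the factor is 30/28 = 1.07. With 35 for 28 (10.2), it is 35/28 = 1.25. If the gap contains no early failures, this source of inflation is absent (factor 1).

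**The case against.** **Evaluability is not benefit.** A reader might infer that anyone without PD at the first scan counts as benefiting. The text does not support that. The two-month rule sets the denominator, and the sentence before it in 6.3 still requires 12 weeks of SD. A patient with SD at week 8 and PD at week 10 is evaluable and has no benefit on either convention. This stands. What remains is the missing classification rule and the literal exclusion of early failures.

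**The interim figures may be right.** A reader might infer that they are shown to be too high. They are not: the row sets only a minimum of 2 months, and all four SD patients may have reached 12 weeks. Nor does PD at week 16 alone produce the lower bounds, because on the time-to-PD convention those patients still count. This also stands, which is why the result is a range.

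**Scans are not confined to weeks 8 and 16.** They continue at week 24 and beyond, and an off-treatment scan can fall between weeks 8 and 16. That settles some patients but not the general rule.

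**The response criteria may supply the convention.** Section 10.3 refers to RECIST 1.1 guidelines, which are not reproduced in full. Section 6.1.3 gives the categories with no rule for timing SD, so the protocol itself leaves it open.

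**The immune-related rate is separate by design.** Section 6.1.4 says "We will define immune-related clinical benefit rate as immune-related stable disease (irSD), irPR, or irCR", with no minimum duration. A reader might call this a contradiction, but irRECIST is stated to be investigational and the measure has its own name. Aligning its duration is optional.

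**The impact is small.** CBR is unpowered and drives no decision. Section 1.7.3 leads with ORR, and the expansion cohort is judged on ORR. This is correct and limits the weight of the point.

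**Conclusion.** The point holds and should be corrected, at the level of a secondary endpoint. CBR as written cannot be computed in one agreed way: the SD threshold sits midway between scheduled scans with no counting rule, and the evaluability sentences conflict. Taken literally, the CBR denominator omits early failures and so biases the rate upward, by an amount that the documents do not allow one to calculate.

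The interim CBRs are upper bounds for the defined endpoint, which lies in 16.7–38.9% (all), 42.9–71.4% (TNBC) and 0–18.2% (ER+). These bounds assume the table's response categories as given, including the pseudoprogression patient recorded as PD, and keep its denominators of 18, 7 and 11. Any treated patient already left out as not evaluable would lower them.

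A reader might extend the point to the primary analysis. ORR, the Simon two-stage rule and the Bayesian expansion rule do not use SD duration or the CBR denominator, so this defect leaves them unaffected.

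**What to change.** - **Definition (2.2.3, 6.3, 10.1, 10.3).** Clinical benefit is a best response of CR or PR at any visit before progression or, in patients without CR or PR, a week 16 scan within its visit window showing no PD.
- **Failures.** Count treated patients without CR or PR who have PD or die by week 16, or have no week 16 assessment, as no benefit. Delete the two-month evaluability rule for CBR.
- **Evaluability.** Reconcile the week 16 sentence in 10.1 with the week 8 sentence in 10.2.
- **Interim table (1.7.3).** Recompute the CBR row on this definition, or relabel it as disease control at first scan.
- **Optional.** Apply the same duration to irSD in 6.1.4.

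The cost is wording in a few sections and re-tabulation of 18 patients from scheduled scans. No new scans are needed, so the study's closure to accrual (Appendix E, Amendment 12) is no obstacle. There are three downsides. CBR may fall. The SD threshold works as about 16 weeks, stricter than the stated 12 and adopted after general-cohort results were known, so the change should be dated and disclosed. The CBR population also becomes treated patients rather than the evaluable patients named in 10.3, and the text should say so.

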#### **6.4 Exploratory Endpoints**

Biomarkers predictive of response include assessment of serum or tissue-based markers including but not limited to: circulating tumor DNA, immunohistochemical expression of PD-L1; TILs; changes in tissue and peripheral T cell receptor sequencing, mutational and neoantigen burden, and immune-related candidate gene signatures at baseline.

To determine the response rate (RR) and duration of response (DoR) of next line therapy after progression on durvalumab/ tremelimumab study regimen, for those patients who are able to submit detailed follow up data about subsequent treatment and response.

### **7.0 ADVERSE EVENTS**

This study will be conducted in compliance with the Data Safety Monitoring Plan (DSMP) of the Robert H. Lurie Comprehensive Cancer Center of Northwestern University (please refer to Appendices for additional information). The level of risk attributed to this study requires high level monitoring, as outlined in the DSMP. In addition, the study will abide by all safety reporting regulations, as set forth in the Code of Federal Regulations.

#### **7.1 Adverse Event Monitoring**

Adverse event data collection and reporting, which are required as part of every clinical trial, are done to ensure the safety of subjects enrolled in the studies as well as those who will enroll in future studies using similar agents. Adverse events are reported in a routine manner at scheduled times during a trial (see Section 5 for time points). In addition, certain adverse events must be reported in an expedited manner to allow for optimal monitoring and patient safety and care.

All patients experiencing an adverse event, regardless of its relationship to study drug, will be followed until:

- the adverse event resolves or the symptoms or signs that constitute the adverse event return to baseline;
- any abnormal laboratory values have returned to baseline;
- there is a satisfactory explanation other than the study drug for the changes observed; or
- death.

Adverse events and serious adverse events will be recorded from time of signature of informed consent, throughout the treatment period and including the follow-up period (90 days after the last dose of durvalumab + tremelimumab, or until resolution of AEs).

**During the course of the study all AEs and SAEs should be proactively followed up for each subject. Every effort should be made to obtain a resolution for all events, even if the events continue after discontinuation/study completion.**

If a subject discontinues from treatment for reasons other than disease progression, and therefore continues to have tumor assessments, drug or procedure-related SAEs must be captured until the patient is considered to have confirmed PD and will have no further tumor assessments.

The investigator is responsible for following all SAEs until resolution, until the subject returns to baseline status, or until the condition has stabilized with the expectation that it will remain chronic, even if this extends beyond study participation.

AstraZeneca/MedImmune retains the right to request additional information for any subject with ongoing AE(s)/SAE(s) at the end of the study, if judged necessary

## 7.2 Definitions & Descriptions

### 7.2.1 Adverse Event

The International Conference on Harmonization (ICH) Guideline for Good Clinical Practice (GCP) E6 (R1) defines an adverse event (AE) as any untoward medical occurrence in a patient or clinical investigation subject administered a pharmaceutical product and which does not necessarily have a causal relationship with this treatment. An AE can therefore be any unfavorable and unintended sign (including an abnormal laboratory finding), symptom, or disease temporally associated with the use of an experimental intervention, whether or not related to the medicinal product.

Recording of AEs should be done in a concise manner using standard, acceptable medical terms. In general, AEs are not procedures or measurements, but should reflect the reason for the procedure or the diagnosis based on the abnormal measurement.

An AE includes but is not limited to any clinically significant worsening of a subject's pre-existing condition. An abnormal laboratory finding (including ECG finding) that requires an action or intervention by the investigator, or a finding judged by the investigator to represent a change beyond the range of normal physiologic fluctuation, should be reported as an AE.

Adverse events may be treatment emergent (ie, occurring after initial receipt of investigational product) or nontreatment emergent. A nontreatment-emergent AE is any new sign or symptom, disease, or other untoward medical event that begins after written informed consent has been obtained but before the subject has received investigational product.

Elective treatment or surgery or preplanned treatment or surgery (that was scheduled prior to the subject being enrolled into the study) for a documented pre-existing condition, that did not worsen from baseline, is not considered an AE (serious or nonserious). An untoward medical event occurring during the prescheduled elective procedure or routinely scheduled treatment should be recorded as an AE or SAE.

The term AE is used to include both serious and non-serious AEs.

